This proposal aims to address the issue of early readmission to psychiatric units by enhancing predictability and understanding of intervention strategies to reduce readmission rates.

Trial registration

KEY WORDS

Early readmission, discharge intervention, psychiatric unit, continuity of care, psychotherapy group, recovery.

INTRODUCCIÓN

Discharge from hospital after admission to a Mental Health Inpatient Unit is a particularly sensitive time, which can place the individual in a situation of great vulnerability. The transition from admission to the patient's usual environment and the return to care in his or her unit of reference, mostly the Community Mental Health Unit (CMHU), represents a major challenge for both the individual and the health institutions, often compromising continuity of care and leading to repeated hospital admissions, a phenomenon known as the "revolving door" (1).

The rate of early readmissions in a short psychiatric hospitalization unit can be a negative indicator of quality of care, resulting in a deficient attention to the needs and peculiarities of users that has important repercussions for patients, their caregivers and the health system (2). A correct interpretation of the impact that early readmission can have on the quality of care must always be based on a community-centered care model (3), where psychiatric hospitalization is a measure of last resort and to some extent can be considered a therapeutic "failure" in a large number of patients.

Readmission rates vary widely depending on the type of measure employed, with approximately 1 in 7 patients discharged from an acute psychiatric care unit estimated to be readmitted within 30 days and up to 40% readmitted within 1 year. In this regard, numerous studies have been conducted around the world to discern the variables that influence hospital readmission rates and to determine which specific interventions are effective in reducing readmission rates (4,5).

The factors influencing the risk of readmission have been studied for decades. There are variables that have frequently been associated with a higher recurrence of hospitalizations, some of them related to clinical and sociodemographic aspects of the patient, such as poor treatment adherence, substance abuse, psychiatric diagnosis of psychosis or affective disorder, suicidal ideation, gender, marital status, social isolation, etc., and others more associated with institutional factors, such as the involuntary nature of admission, length of stay, or the availability of an adequate care plan and community therapeutic resources after discharge (6).

Regarding interventions, there is an enormous heterogeneity in the available evidence, due both to the diversity of post-discharge interventions that have been developed in this regard, and to the variability of measures and results that are taken as a reference to assess their efficacy (1). In some studies, the number of readmissions within different time frames (30 days, 6 months, one year) has been used as the dependent variable, while in others, the effectiveness of post-hospitalization intervention is assessed using other parameters such as the duration of future hospitalizations or the reduction in suicidal ideation or attempts. Scientific knowledge on the

subject yields promising results. However, this heterogeneity makes it difficult to draw clear conclusions about this issue.

In a systematic review carried out in 2019, a classification of these interventions has been made based on a clustering method and according to their key components (1), and they can be divided into: Critical Time Interventions (CTI), Transitional Discharge Model (TDM), peer support, contact-based interventions, role-based interventions, psychoeducational interventions, multicomponent interventions and others. From this and other studies, it is evident that interventions based on the Transition to Discharge Model have yielded significant results in reducing readmissions, achieving earlier discharges from hospital units, and improving therapeutic adherence.

Interventions with a psychoeducational and skill-building profile have shown good results in reducing readmission rates, promoting self-management and behavioral regulation, and increasing levels of emotional well-being and symptom reduction. Post-discharge interventions focused on a single component in isolation (such as contact-based, peer support, role-based, pharmacological management, etc.) by themselves demonstrate inconsistent results regarding readmission reduction, varying across studies (1,7).

In summary, all studies reporting significant effects include elements of intensive case management, Cognitive Behavioral Therapy, and psychoeducation, either in combination or linked to another element such as peer support. The success of psychoeducational interventions and those focusing on the therapeutic relationship underscores the importance of addressing personal issues and emotional elements during care transition when aiming to reduce psychiatric readmissions (7).

On the other hand, clinical practice guidelines (CPG) for addressing severe mental illness emphasize the importance of psychosocial rehabilitation in the recovery process. This involves therapeutic actions aimed at training and developing personal and social skills, psychoeducational strategies with families and users, building social networks, and promoting personal autonomy, among others. The objective is to enhance the psychosocial functioning of individuals with severe mental illness and facilitate their adaptation and maintenance within the community (8,9). From all of this, it becomes clear the importance of conducting a multicomponent therapeutic approach that combines elements aimed at ensuring continuity of care and effective and intensive case management, with those aimed at providing a supportive bond and environment to address personal and emotional difficulties. This approach strengthens the patient's skills and support system, enhancing social support networks (7,9).

The aim of this study is, firstly, to create a tool for assessing the risk of early readmission that allows for stratification of admitted patients according to their risk level, based on the analysis of clinical and sociodemographic variables. The second objective is to implement an intervention program tailored to each risk level, involving coordination among all involved mental health units and a specific intensive program for patients at higher risk.

METHODS

- **Aims**

- General**

- To assess whether a Multicomponent Discharge Transition Intervention reduces the risk of early readmission compared to a control group following standard treatment.

- Secondary**

- To check whether the risk of early readmission is reduced with respect to the previous year in the experimental group and in the control group.

- To check whether early readmission rates are reduced in the experimental group compared with the control group and with respect to readmission rates in the previous year.

- Identify risk factors that are associated with early readmissions.

- To test whether a scale for estimating the risk of early readmission has adequate psychometric characteristics for such estimation.

- To test whether a Post-Discharge Recovery Support Psychotherapy Group improves outcome on measures of recovery, functioning, subjective well-being, social support, and satisfaction with mental health treatment in patients at high risk of early readmission.

- To test whether the Transition to Discharge intervention also reduces the risk of frequent readmission (revolving door).

- **Design**

The present study is a quasi-experimental cluster clinical trial aimed at assessing the efficacy of a multicomponent discharge transition program for the reduction of early readmissions in a MHHU. The development of this study consists of two distinct parts or elements:

To carry out the main objective, a quasi-experimental design with a control group will be used, and within the intervention, an early readmission risk assessment scale will be created to categorize patients into different risk levels.

In addition, a study will be conducted to assess the predictive value and validity of the early readmission risk rating scale and to study the risk factors for early readmission.

- **Setting**

The present study will be carried out in the MHHU of the Regional University Hospital (RUH) of Malaga, a public hospital of the Andalusian Health Service. In addition to the Mental Health Clinical Management Unit of the HRU of Málaga, this MHHU is a reference for two other regional hospitals in the province of Málaga: The Málaga East Axarquía Hospital and North Málaga Health Management Area. The Mental Health Clinical Management Unit of the RUH of Malaga, according to figures from the 2022 database of users, serves a reference population of 336,968 people, while 150,823 people depend on the Mental Health Clinical Management La Axarquía and 109,958 depend on the Mental Health Clinical Management North of Málaga, resulting in a reference population of 597,749 people for hospitalization resources.

The MHHU has 40 beds in double rooms and is divided into two functional units. The access routes to hospitalization in this unit are admission from the Emergency Services, after evaluation by a psychiatrist, and programmed admission from another unit. The average occupancy rate is two thirds (28 beds) of the total capacity and the average stay in the year 2022 was 13.7 days, with a total number of admissions of 838. The data collected at the RUH of Malaga indicate an early readmission rate of 15.08% in the year 2022, using a time reference of 30 days until readmission.

The Spanish public health system is functionally organized into levels, with Primary Care comprising the first level and Ambulatory Specialized Care and hospital Emergency Services comprising the second level of care. The third level of care consists of hospital units with a high degree of specialization. The proposed intervention will primarily take place in the hospitalization unit (third level), as well as in the community-based outpatient care facilities

affiliated with said hospital, including the North Guadalmedina and Central Malaga Community Mental Health Units (second level).

- **Intervention and control group**

Intervention group

The intervention program is based on the Discharge Transition Model for the prevention of hospital readmission in Mental Health. For its development, a multidisciplinary readmission commission was established, comprised of professionals from various categories and from different Mental Health facilities. The aim was to address this issue in detail and actively participate in the review of available evidence and decision-making regarding the development and implementation of the current program.

This is a multicomponent program that initially involves the development of a scale to assess the risk of readmission for each patient, followed by its systematic application. This allows for stratification of patients according to their risk of early readmission and adaptation of the intervention to the needs of each risk level. The intervention includes elements aimed at promoting continuity of care after discharge, transitioning back to the community setting, as well as elements aimed at enhancing personal and emotional resources through psychotherapeutic approaches. The following describes the different components of this intervention program.

Construction of the Early Readmission Risk Scale

For the preliminary analysis of risk factors associated with readmission, a retrospective observation will be conducted. This will involve analyzing all episodes from the previous calendar year stored in the database of the MHHU of the RUH of Malaga, provided that the records are complete. "Cases" will be selected from episodes that resulted in readmission within 30 days post-discharge, while an equivalent number of "controls" will be randomly selected through simple random sampling. Following this analysis, a measurement instrument will be developed to determine the risk of early readmission for all patients admitted to the MHHU.

A literature search was conducted to identify variables that have been associated with readmission and early readmission in other populations. The following variables were selected

for analysis in the reference population: Sociodemographic factors (sex, age, marital status, legal incapacity, employment status, criminal history, and social functioning), psychiatric history (previous admissions, emergency service visits in the twelve months prior to admission, history of suicide attempts, attendance at community nursing follow-ups in the six months prior to admission, and somatic comorbidity), reasons for admission (presence of hetero- or auto-aggression or deficits in self-care), clinical characteristics (primary diagnosis, substance use, non-adherence to follow-up in the previous 12 months, and non-adherence to treatment up to one month before admission), admission characteristics (urgent or scheduled access route and length of stay), and discharge measures (coordination with referring physician in the CMHU and prescription of depot medication).

During admission to the hospitalization unit, all users must have the aforementioned Early Readmission Risk Scale of the MHHU of the RUH of Malaga administered. This will allow for the classification of patients according to their risk level, establishing defined cutoff points, resulting in three categories: Patients at low risk, medium risk, and high risk. This scale will be completed by the referring physician during the initial assessment interview upon admission to implement the proposed measures for each risk level. Additionally, the referring physician will establish contact with the case management figure responsible for the program for the referral of cases with a score indicative of a high risk of early readmission or patients with early readmission within 30 days post-discharge.

Intervention measures based on the risk of early readmission

For patients classified in the low-risk group, general measures would be applied. For patients in the medium-risk group, reinforced measures would be implemented. Lastly, for patients considered to be in the high-risk group, intensive case management measures would be applied, and if they meet the inclusion criteria, they would be included in the Post-Discharge Group Psychotherapeutic Intervention.

1. General measures

The following measures would be applied to patients with a low risk of readmission:

-Ensure coordination between physicians during admission and a follow-up appointment within 7 days.

-If the patient presents substance abuse, ensure an appointment at the Provincial Drug Dependency Center (PDC) upon discharge and record the date in the discharge report.

-If the patient presents social impairment, refer them to a Social Worker at the MHHU during admission and initiate a social history.

2. Reinforced measures

The following measures would be applied to patients with a medium risk of readmission. In addition to the previous measures, the following would be incorporated:

-Schedule at least three follow-up appointments: one (via telephone) with a psychiatrist from the MHHU within 24 hours post-discharge, and two at the Community Mental Health Unit: the first within 7 days and the second between days 21 and 30.

-If the patient presents social impairment, schedule an appointment with a social worker from the Community Mental Health Unit within 14 days post-discharge.

-If the patient has a Severe Mental Disorder, schedule a nursing visit during their stay at the MHHU.

3. Intensive measures

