In the analysis for the creation of the early rehospitalization risk scale, a univariate logistic regression analysis will be used. For the final selection of factors, a forward stepwise multivariate analysis will be performed, introducing variables with greater statistical significance. Finally, a scale will be developed to measure the risk of early rehospitalization in each admission episode, whose sensitivity and specificity will be tested beforehand using a receiver operating characteristic (ROC) curve. The construction of the scale will follow the procedure outlined in detail in Sullivan et al. (23).

To evaluate the differences between the intervention group and the control groups, a univariate and multivariate mixed logistic regression analysis will be conducted, introducing potential confounding variables (unit occupancy, age, sex, and the variables used in the scale for estimating the risk of early rehospitalization). To assess potential differences in Core Om, Duke-unk-11, PSP, and QPR among patients participating in the Post-Discharge Recovery Support Psychotherapy Program, the paired Student's t-test for repeated measures or the non-parametric Wilcoxon signed-rank test for a single sample will be used.

DISCUSSION

The present research study aims to analyze the risk factors for early rehospitalization of patients discharged from a short-term psychiatric hospitalization unit. Based on this information, the goal is to stratify the risk and direct more intensive therapeutic measures to those individuals with a higher likelihood of rehospitalization to reduce early rehospitalization rates.

Thus, determining the risk of psychiatric rehospitalization for individual patients is a critical step in efforts to address the potentially avoidable high rate of this negative outcome, as highlighted in the READMIT study (4). This study conducted in Canada succeeded in providing a framework to identify patients at high risk of rehospitalization through the development of a prognostic index with moderate discriminative capacity.

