One of the main strengths of our study is that it will be conducted in a real-world context, and the instrument to be used for patient stratification will be developed in the same population where it will subsequently be applied, reducing the possibility of cultural factors or context-specific factors biasing the validity of the risk scale. Additionally, the individuals involved in the care of hospitalized patients will work directly on this instrument and subsequently on the intervention to be developed, which will consist of multiple components.

Among the challenges of the study are being able to fulfill all the measures outlined in the intervention program, as external factors may condition it: shortage of hospital beds, premature discharges or voluntary discharges, staffing deficits, lack of community resources, etc. Additionally, many factors associated with early rehospitalization may be difficult to address within the program itself: substance abuse, homelessness, difficulties associated with group work, cognitive deficits, heterogeneity of participating subjects, etc.

One of the major limitations of the study is that it will only be conducted in one inpatient unit, so generalization of the results to other settings will be problematic. As reflected in previous studies, such as the one cited above, its findings have not been able to effectively discriminate potentially readmitting patients in subsequent studies conducted with different populations (24). This tells us about the complexity of the phenomenon of early readmission, an event that is difficult to predict, multicausal and involves factors that require a complex approach (25).

Finally, an important aspect is that the treatment allocation is not randomized, which may introduce biases that will be addressed by using two control groups. However, there may potentially be confounding variables that will be considered in the analysis. Given these limitations, if this study yields satisfactory results, a likely future direction could be to develop a randomized, multicenter clinical trial at the regional or state level.

LIST OF ABBREVIATIONS

CAT: Client's Assessment of Treatment
CMHU: Community Mental Health Unit
CPG: Clinical Practice Guidelines
CTI: Critical Time Interventions
MHHU: Mental Health Hospitalization Unit
PDC: Provincial Drug Dependency Center
PSP: Personal and Social Performance Scale
QPR: Recovery Process Questionnaire
RUH: Regional University Hospital

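### Involuntary admission and homelessness, both linked to readmission by the plan itself, are neither scale candidates nor named confounders, so any imbalance in them would not be directly adjusted

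*Combined protocol and SAP*

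**What the plan says.** The Introduction separates patient-level from institutional influences on repeated hospitalisation. Among the latter it names "institutional factors, such as the involuntary nature of admission, length of stay". The Discussion, describing the challenges of the study, says that "many factors associated with early rehospitalization may be difficult to address within the program itself: substance abuse, homelessness" and other problems may be hard for the programme to deal with.

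Under Construction of the Early Readmission Risk Scale, the plan lists the variables to be analysed. The three groups closest to the two factors are:

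- "Sociodemographic factors (sex, age, marital status, legal incapacity, employment status, criminal history, and social functioning";
- "reasons for admission (presence of hetero- or auto-aggression or deficits in self-care";
- "admission characteristics (urgent or scheduled access route and length of stay".

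Data analysis describes how candidates reach the scale: after univariate screening, "a forward stepwise multivariate analysis will be performed, introducing variables with greater statistical significance". The same section gives the mixed logistic model for comparing the groups, "introducing potential confounding variables (unit occupancy, age, sex, and the variables used in the scale for estimating the risk of early rehospitalization".

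Participants and recruitment assigns patients by the hospital to which their community unit belongs. Study variables makes the main outcome the early-readmission risk of the experimental group against the control group. The Discussion accepts that non-random allocation may bias the result. Its answer is two control groups and attention to confounders in the analysis, and it names none beyond those in Data analysis.

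**The concern.** Groups defined by catchment can differ in case mix, and covariate adjustment is one of the two defences the plan offers. That adjustment reaches only occupancy, age, sex and whatever the scale retains. A variable outside the candidate list can never become a scale variable, so the two factors stay out of the model even if the plan is followed exactly.

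If involuntary admission or homelessness were more common in one group, the difference in readmission it produces would be read as part of the programme effect. This could go in either direction. An imbalance is plausible: the Setting section places the intervention in an area that includes the Central Málaga community unit, while the controls come from two other areas of the province. Plausibility is all the documents offer. Without the two fields, the investigators also could not check whether the groups are balanced. One of the secondary aims is to identify risk factors for early readmission, and two that the plan mentions would go unexamined.

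**Working it through.** **Step 1: text check.** The plan states no sample size, power or target effect, so it has no figure of its own to reproduce. The check sets its lists side by side.

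| Factor | Linked to readmission in | Scale candidate? | Named confounder? | Nearest listed items |
|---|---|---|---|---|
| Involuntary admission | Introduction | No | No | Urgent/scheduled route, aggression, legal incapacity |
| Homelessness | Discussion | No | No | Social functioning, self-care deficit |

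The nearest items are proxies. The Setting section describes the access routes as emergency or programmed, and an urgent admission may be voluntary. Legal incapacity is a standing status, not the legal basis of one admission. Social functioning does not record housing. A proxy helps only if stepwise selection retains it.

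Most other factors in the Introduction do reach the candidate list: adherence, substance use, diagnosis, sex, marital status and length of stay. Suicidal ideation and social isolation do so only through near equivalents (suicide attempts, social functioning). No reason is given for leaving out the two factors at issue.

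**Step 2: inputs for an illustration of size.**

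- From the Setting section: 838 admissions in 2022, a 30-day readmission rate of 15.08%, and reference populations of 336,968 (Regional Hospital area) and 597,749 (total).
- Assumed: admissions proportional to population; control risk 15.08%; independent episodes; no programme effect; no capture by proxies.
- Assumed, with nothing in the documents to set them: the factor's odds ratio and its prevalence in each group.

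**Step 3: standard error.**

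Episodes: 838 × 336,968 / 597,749 = 472 experimental; 838 − 472 = 366 control.

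SE(log OR) = √[1/(472 × 0.1508 × 0.8492) + 1/(366 × 0.1508 × 0.8492)] = √(0.01654 + 0.02134) = 0.195.

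**Step 4: spurious odds ratio.** Let p0 and p1 be the factor's prevalence in the control and experimental groups. Solve for b in

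p0 × expit(b + ln OR) + (1 − p0) × expit(b) = 0.1508,

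then replace p0 by p1 to get the experimental risk with no true effect. The false-positive rate is P(|Z + ln(spurious OR)/0.195| > 1.96).

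Worked case, OR 2, 20% experimental and 30% control:

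- b = −1.972, so the risk is 12.21% without the factor and 21.77% with it.
- Control: 0.3 × 0.2177 + 0.7 × 0.1221 = 0.1508.
- Experimental: 0.2 × 0.2177 + 0.8 × 0.1221 = 0.1412.
- Spurious OR = (0.1412/0.8588)/(0.1508/0.8492) = 0.93.
- Shift = ln(0.926)/0.195 = −0.39 standard errors; false-positive rate 6.8%.

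| Factor OR | Prevalences in the two groups | Spurious OR, by direction of imbalance | False-positive rate |
|---|---|---|---|
| 2.0 | 30% and 30% | 1.00 | 5.0% |
| 1.5 | 20% and 30% | 0.96 or 1.04 | 5.6% |
| 2.0 | 20% and 30% | 0.93 or 1.08 | 6.8% |
| 2.0 | 5% and 15% | 0.92 or 1.09 | 7.1% |
| 2.0 | 20% and 40% | 0.86 or 1.16 | about 12% |

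In the three 10-point rows the risk moves by about 0.6 to 1.1 percentage points.

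**The case against.** The strongest answer is that a risk factor confounds only if it is unevenly distributed, and no section gives the frequency of either factor by catchment or by year. This stands. A reader might infer that the plan leaves known case-mix differences unadjusted. The documents do not support that: they show two risk factors, not a difference between groups.

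A second answer is the design. The plan also compares the Regional Hospital's patients with the previous year and looks at the change in both groups, and differences between areas that are stable over time would not bias a within-area comparison. This stands in part. The main outcome remains experimental against control, Data analysis specifies no group-by-period term, and changes in either factor between years would remain.

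Third, the two areas share one inpatient unit, so differences in ward practice are limited. This is fair, but the patients' legal status on admission and their housing can still differ by area.

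Fourth, the sources are looser than a covariate list. The Introduction speaks of recurrent hospitalisation rather than 30-day readmission, the Discussion mentions homelessness in a list of practical challenges, and the candidates were chosen after a literature search. This tempers the point. The plan still associates both factors with readmission and does not explain their absence.

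Finally, proxies may absorb part of any effect, and the documents do not say whether the records hold either field. Both are right. The figures above therefore take no account of proxy capture, and the remedy has to be conditional on the records.

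**Conclusion.** The gap is real but limited. Two factors that the plan itself associates with readmission can enter neither the scale nor the adjusted comparison, so any imbalance in them between catchments or years would not be directly adjusted. Whether there is an imbalance is unknown. The bias is nil if prevalence is equal. It is small for a 10-point imbalance in a factor with an odds ratio of 1.5 to 2, and becomes noticeable only under the largest imbalance tried (20 points with an odds ratio of 2).

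These sizes rest on assumed odds ratios and prevalences, a population-proportional split of the 2022 admissions and no capture by proxies. Because the plan states no target effect, the sizes cannot be set against a difference the trial is meant to detect. It would go too far to conclude that the comparison is biased, or biased in a particular direction. The point supports a cheap improvement to the covariate list and does not by itself invalidate the analysis.

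**What to change.** Add two items to the data extraction, valued at each index admission, for all groups and both years, wherever the electronic records hold them:

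1. voluntary or involuntary status of the admission;
2. homeless or no fixed address (yes/no).

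In Data analysis, pre-specify both as covariates in the between-group mixed logistic model, whether or not the scale keeps them. If a field turns out not to be reliably recorded, state this and list it as an unadjusted confounder in the limitations.

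Entering the two items as scale candidates is optional. Scale development uses complete records only, so a poorly recorded field could cost episodes there.

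The cost is some chart look-up, mainly for previous-year episodes, possible missing values, and two degrees of freedom in the model. No treatment rule changes.
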